### **Serum hepatic fibrosis indices**

Serum hepatic fibrosis indices (including FIB-4, APRI, and NFS) will be determined at Screening, Baseline, and Months 6 and 12 in Part 1, and at Screening, Baseline, Months 6 and 12, and every 12 months thereafter in Part 2.

APRI is calculated using the formula:

$$\text{APRI} = (\text{AST level [ULN]} / \text{platelet counts [10}^9\text{/L]}) \times 100$$

An APRI index of  $\leq 0.50$  indicates the absence of significant fibrosis and an index of  $> 1.50$  indicates the presence of significant fibrosis.

NFS is a validated simple scoring system consisting of routinely measured and readily available clinical and laboratory data to categorize NAFLD patients with and without advanced fibrosis:

$NFS = -1.675 + 0.037 \times \text{age (years)} + 0.094 \times \text{BMI (kg/m}^2\text{)} + 1.13 \times \text{IFG/diabetes (yes = 1, no = 0)} + 0.99 \times \text{AST/ALT ratio} - 0.013 \times \text{platelet (}\times 10^9\text{/L)} - 0.66 \times \text{albumin (g/dL)}$ . FIB-4 is a noninvasive hepatic fibrosis index score combining standard biochemical values, platelets, ALT, AST, and age that is calculated using the formula:

$$\text{FIB-4} = (\text{Age [years]} \times \text{AST [U/L]}) / (\text{platelets [10}^9\text{/L]} \times (\text{ALT [U/L]})^{1/2})$$

A FIB-4 index of  $< 1.45$  indicates no or moderate fibrosis and an index of  $> 3.25$  indicates extensive fibrosis/cirrhosis.

The Enhanced Liver Fibrosis (ELF™) Test is a blood test that provides an ELF Score that delivers information on liver fibrosis severity and will be assessed in this study. The ELF Score is determined by combining in an algorithm, quantitative measurements of by-products of the fibrotic process (hyaluronic acid [HA]), amino-terminal propeptide of type III procollagen [PIIINP]), tissue inhibitor of metalloproteinase 1 [TIMP-1]).

The ELF Score will be determined at Baseline, Month 6, Month 12, and every 12 months thereafter.

The authors analyzed routine demographic, clinical, and laboratory variables to predict presence or absence of advanced fibrosis. Age, hyperglycemia, BMI, platelet count, serum albumin, and AST/ALT ratio were found to be independent indicators of advanced liver fibrosis, so these 6 variables were included in the NFS scoring system. A low cut-off score of -1.455 indicates the absence of advanced fibrosis and a high cut-off score of 0.676 indicates the presence of advanced fibrosis.

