- Proportion of subjects with complete resolution of steatohepatitis (defined as histopathologic interpretation of no fatty liver disease or simple or isolated steatosis with no steatohepatitis) AND no worsening of liver fibrosis (defined as progression of NASH CRN fibrosis stage) at Month 60 relative to the Screening biopsy – (all subjects)
- Proportion of subjects with improvement in fibrosis by at least 1 stage (Ishak system), regardless of effect on steatohepatitis, on liver biopsy at Month 60 relative to the Screening biopsy – (all subjects)
- Proportion of subjects with histopathologic progression to cirrhosis (defined by NASH CRN Fibrosis Stage 4) at Month 60– (all subjects)
- Change from baseline in noninvasive assessments of liver fibrosis (including FIB-4, APRI, NFS, ELF and liver stiffness through TE) over time – (all subjects)

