Time-to-event (Part 2: primary endpoint)	Treatment Period	
 All subjects in mITT analysis set included. Any available adequate liver biopsy after baseline will be used for assessment of components of the clinical endpoint that require a biopsy, no matter when obtained. Subjects with multiple liver biopsies will be included as an event if any (one or more) biopsy meets the definition of the primary endpoint, as determined by the adjudication committee. Subjects who do not have an evaluable liver biopsy at both Screening and post-baseline will be included in the analyses as having an event only if they meet a component that does not require a biopsy; otherwise they will be included as not having an event and censored at the last visit. Subjects with partial follow-up data will be included as an event if they meet the criteria for any component of the primary efficacy endpoint, and as a nonevent if they do not meet the criteria for any component. A sensitivity analysis assuming data are missing not at random will be reported. An additional sensitivity analysis imputing an event at the time of censoring will also be reported, although it is anticipated that this analysis will not be informative unless many subjects discontinue due to unobserved NASH progression, which cannot be known.
CFB ANCOVA	Months 6 and 12 in Part 1, and Month 12 and annually thereafter in Part 2 (Month 6 in Part 2 for some endpoints)	
 If missing covariates (including baseline if applicable) 
 Subject excluded Observed data for mean absolute change and relative change from baseline to the times specified in the endpoints will be analyzed. There is no imputation for missing data.
Multiple imputation (Part 1: primary efficacy endpoint)	Month 12 MAR and MNAR	
A sensitivity analysis for the primary efficacy analysis in Part 1 will use multiple imputation to investigate the impact of missing data under a Missing At Random (MAR) assumption. For this analysis, the Month 12 biopsy results will be imputed for the subjects who do not have an evaluable biopsy after baseline. The imputation model will be defined before Part 1 unblinding to avoid the addition bias.
 
The multiple imputation model will use the MI procedure in SAS, using code such as the following:
 <pre>proc mi data=<inputdsn> seed=1305417 nimpute=100 out=<outputdsn>; class outcome trt; var trt <explanatory> outcome;</pre>

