Occasional bridging fibrosis (< 50% linkage of portal and/or central zones)	3																
Marked bridging fibrosis (> 50% linkage of portal and/or central zones but not yet cirrhosis)	4																
Early or incomplete cirrhosis	5																
Established or advanced cirrhosis	6																

[figure not shown]

Baseline assessments for applicable efficacy endpoints defined as follows:

Table 5-13 Efficacy Endpoint Baseline Definitions

Type of Endpoint	Description	Timing
Part 1: Primary, secondary [REDACTED] Improvement of fibrosis stage (NASH CRN system) on liver histology at Month 12 relative to the Screening biopsy	Fibrosis stage (NASH CRN system) based on Screening biopsy	Screening biopsy result before Baseline visit and before subject is randomized
Part 1: Primary, secondary [REDACTED] Worsening of steatohepatitis (no worsening of lobular inflammation or hepatocellular ballooning grade 2005) on liver histology at Month 12 relative to the Screening biopsy	Steatohepatitis status (lobular inflammation or hepatocellular ballooning grade 2005) based on Screening biopsy	Screening biopsy result before Baseline visit and before subject is randomized
Part 1 and Part 2: Change in baseline in noninvasive assessments of liver fibrosis (FIB-4, APRI, NFS, and ELF score)	Occurs within 3 months before the Baseline visit. Baseline visit is defined as the last available assessment before the date of 1 st dosing (for all efficacy and safety endpoints).	Screening serum hepatic fibrosis indices
Part 1 and Part 2: Change in baseline in noninvasive assessments of liver fibrosis (liver stiffness)	The Screening value (if not performed by TE within 6 months prior to the first day of Screening) will be used as the Baseline value. TE will be performed at Baseline if not performed within 6 months prior to the first day of Screening.	Screening via TE or liver imaging

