Part 1: Primary efficacy endpoint (sensitivity analyses 1)	The primary efficacy endpoint will be performed using the ITT and PP1 populations as sensitivity analyses.	Same as above	Cochran-Mantel-Haenszel (CMH) test, stratified by actual fibrosis stage (2, 3) and T2DM status (presence, absence) at baseline
Part 1: Primary efficacy endpoint (sensitivity analysis 2)	Logistic regression, with fibrosis stage, presence of T2DM, study site as predictors and baseline covariates (to be listed out later) using the mITT analysis set.	Same as above	Logistic regression, with covariates for the stratification factors
Part 1: Primary efficacy endpoint (sensitivity analysis 3)	An assessment of efficacy will also be made using multiple imputation, for scenarios of both assuming missing at random and missing not at random, for the CMH test. Refer to Section 5.1.1.1.5.	Same as above	Multiple imputation

[figure not shown]
Type of Endpoint	Description	Timing	Methodology
Part 1: Primary efficacy endpoint (subgroup analysis)	Refer to Section 5.1.1.5.	Same as above	Cochran-Mantel-Haenszel (CMH) test, stratified by true fibrosis stage (2, 3) and T2DM status (presence, absence) at baseline
Part 1: Secondary efficacy endpoints (binary)	Analysis of other secondary efficacy endpoints of Part 1 will use similar methods to the primary endpoint analysis. Results for the mITT and PP1 analysis sets will be reported for secondary efficacy endpoints.	Same as above	Cochran-Mantel-Haenszel (CMH) test, stratified by true fibrosis stage (2, 3) and T2DM status (presence, absence) at baseline
Part 1: Secondary efficacy endpoints (continuous)	Continuous endpoints will be analyzed with analysis of covariance, with true fibrosis stage (2, 3) and T2DM status (presence, absence) at baseline) included as factors using the mITT and PP1 populations.	Same as above	CFB ANCOVA

[figure not shown]

Type of Endpoint	Description	Timing	Methodology

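### SAP Table 5-4 plans relative change from baseline without visibly exempting the NAFLD fibrosis score, a score that crosses zero, so its relative change has no stable sign or size

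*SAP*

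**What the plan says.** SAP 5.1.1.1.5, Table 5-4, has a row for endpoints handled by CFB ANCOVA. It excludes subjects with missing covariates, rules out imputation, and says: "Observed data for mean absolute change and relative change from baseline to the times specified in the endpoints will be analyzed". The row's timing is "Months 6 and 12 in Part 1, and Month 12 and annually thereafter in Part 2", with Month 6 in Part 2 for some endpoints.

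NFS falls within the row's apparent reach:

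- Protocol 12.3.1.2 lists "Change from baseline in noninvasive assessments of liver fibrosis (including FIB-4, APRI, NFS, ELF and liver stiffness through TE) over time".
- SAP Table 5-13 gives a baseline definition for "Change in baseline in noninvasive assessments of liver fibrosis (FIB-4, APRI, NFS, and ELF score" in both parts.
- Protocol 11.2 sets the visits: "Serum hepatic fibrosis indices (including FIB-4, APRI, and NFS) will be determined at Screening, Baseline, and Months 6 and 12 in Part 1". In Part 2 they are Months 6 and 12 and then every 12 months, which matches the row.
- For the Part 1 secondary endpoints, SAP Table 5-14 says: "Continuous endpoints will be analyzed with analysis of covariance", and names CFB ANCOVA as the method.

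Protocol 11.2 defines NFS as a linear score that starts "NFS = -1.675 + 0.037" times age. It adds terms for BMI, impaired fasting glucose or diabetes, and AST/ALT, and subtracts terms for platelets and albumin. It interprets the score thus: "A low cut-off score of -1.455 indicates the absence of advanced fibrosis and a high cut-off score of 0.676" marks its presence.

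**The concern.** A percentage change has a meaning only when the scale has a true zero and baselines are well away from it. NFS meets neither condition. Its zero is an accident of the intercept and lies between the two diagnostic cut-offs. A higher score means more fibrosis, so a fall is an improvement. Dividing a fall by a negative baseline turns it into a positive percentage, which reads as worsening. Dividing by a baseline near zero gives a huge value of either sign.

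A mean of such values does not estimate a treatment effect. If the row is followed as written, two NFS comparisons are produced. One is sound; the other has an essentially arbitrary direction and can contradict the first and the other fibrosis markers. No visible rule says which one governs.

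**Working it through.** The plan states no sample size, power or alpha for NFS, so there is no figure of its own to reproduce.

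**Step 1. Arithmetic from the protocol's cut-offs.** The SAP gives no formula, so take relative change as 100 × (post - baseline) / baseline. Apply a fall of 0.30 points:

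- baseline -1.455: -0.30 / -1.455 = +20.6%
- baseline +0.676: -0.30 / 0.676 = -44.4%
- baseline -0.05: -0.30 / -0.05 = +600%
- baseline +0.05: -0.30 / 0.05 = -600%

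The 0.30 and the two baselines near zero are illustrations. The sign reversal below zero holds for any change.

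**Step 2. Where baselines may lie.** The documents give no baseline NFS. Age 54.1 is the Phase 2b mean (Protocol 5.3.3). BMI 34, AST/ALT 0.8, platelets 230 and albumin 4.4 are assumptions. Without diabetes:

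-1.675 + 0.037×54.1 + 0.094×34 + 0.99×0.8 - 0.013×230 - 0.66×4.4 = -1.675 + 2.002 + 3.196 + 0.792 - 2.990 - 2.904 = -1.58

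With diabetes, add 1.13: -0.45.

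Full distributions were then simulated with mean BMI 30-38 (SD 6), mean platelets 200-260 (SD 60), median AST/ALT 0.78, albumin 4.4 (SD 0.3), age SD 11 and 50% T2DM. Between 58% and 93% of baselines were negative, 2-7% lay within 0.1 of zero, and 6-16% within 0.25.

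**Step 3. ANCOVA on both scales.** The setting was 800 vs 400 (the planned Part 1 arms), assumed SD of change 0.6, adjustment for baseline NFS and T2DM, two-sided 0.05, three baseline settings and 1,000 replicates each. Ranges are across the baseline settings.

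| True benefit (points) | Absolute change: rejects | Relative change: rejects | Relative change: estimate favours CVC |
|---|---|---|---|
| 0.10 | 76-79% | 2-3% | 46-49% |
| 0.15 | 98-99% | 2-4% | 41-49% |
| 0.30 | 100% | 3-7% | 37-49% |

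With absolute change the estimate favoured CVC in 99-100% of replicates. Dividing by the absolute value of baseline repairs the sign subject by subject but not the instability: it rejected in 6-30% of replicates and favoured CVC in 66-88%.

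**Step 4. Second set of assumptions.** This used 733 vs 366, which corresponds to the 1,293 randomised in Part 1 (SAP 5.2.1) × 0.85 = 1,099, split 2:1. The 15% is the plan's missing-biopsy rate; NFS needs no biopsy, so it is only a rough allowance here. Over effects of 0.1 to 0.3 and SDs of change of 0.4 to 0.8, absolute change rejected in 49-100% and relative change in 2-4%. In the central case (effect 0.2, SD 0.6), the relative-change estimate had the wrong sign in 54% of trials. Moving the mean baseline to -1.4 or 0.0 did not alter the picture.

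**Step 5. Hand check of the absolute-change power.**

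- SE = 0.6 × √(1/800 + 1/400) = 0.0367. For a 0.10 benefit, z = 0.10 / 0.0367 = 2.72, and power ≈ Φ(2.72 - 1.96) = 78%.
- Least favourable case: SE = 0.8 × √(1/733 + 1/366) = 0.0512. Then z = 0.10 / 0.0512 = 1.95, and power is about 50%.

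Both agree with the simulations.

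**Why relative change fails.** Given baseline b, the variance of change/b is proportional to 1/b². If the baseline distribution has positive density at zero, the mean of 1/b² diverges. The few subjects nearest zero then dominate the estimate, and neither a larger trial nor the baseline covariate cures this.

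**The case against.** Several points on the other side have force.

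- **The sentence sits in a missing-data table.** SAP Table 5-2, which defines the CFB ANCOVA, models only the change-from-baseline value and never mentions relative change. That an ANCOVA will be run on relative change is therefore an inference from the row's label. This lowers certainty. But the sentence is still the visible instruction on which quantities are analysed, and a programmer following it has neither a formula nor an exemption.
- **Redacted text may settle it.** The row defers to times specified in the endpoints. Parts of SAP 4.2 and Tables 5-13 and 5-14 are not visible, and the visible numbering runs from 5.1.1.3.1 to 5.1.1.3.3. A definition or limit could stand there. This stands as a caveat.
- **A reader might infer that every change-from-baseline marker is affected.** The documents do not support that. SAP 5.2.2 assigns ELF and PRO-C3 descriptive statistics, and FIB-4, APRI and liver stiffness are strictly positive, so relative change is workable for them.
- **A reader might infer that NFS is a formal secondary endpoint**, from its place in Protocol 12.3.1.2. The Part 2 secondary lists in the protocol synopsis, Protocol 6.2 and SAP 4.2 show only histology and safety (with time-to-event outcomes as the primary). The marker items in 12.3.1.2 follow a gap in the text, where a lower-tier heading may have been removed. NFS is better described as supportive.
- **The power figures rest on assumed inputs** for a comparison the trial was not sized for. They illustrate the noise and do not measure a planned property of the trial.

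**Conclusion.** The point holds for NFS, with moderate confidence. The sign reversal follows from the protocol's own formula and cut-offs and needs no population assumption. It is a stated rule that gives a misleading result when followed, and not only a missing detail.

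The size of the noise depends on assumed baseline distributions, spread of change and treatment effect. Within every range tried, relative change rejected at about the rate expected with no effect or not much above it, in near-random direction, while absolute change on the same data performed normally.

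A reader might go further and infer that the trial's conclusions are at risk. They are not. The alpha-controlled tests are the Part 1 primary and key secondary endpoints and the Part 2 primary endpoint (SAP 5.1.1.3.1 and 5.1.1.3.3). The valid NFS analysis, absolute change, is already planned in the same sentence. What is at stake is one supportive comparison that cannot inform and could mislead.

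**What to change.** In the CFB ANCOVA row of SAP Table 5-4:

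1. Define relative change and list the markers it applies to: FIB-4, APRI and liver stiffness, all strictly positive.
2. Preferably analyse it as log(post/baseline) with log baseline as covariate, and report the result as a ratio of geometric means.
3. State that NFS is analysed by absolute change only.

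If a redacted section already limits relative change in this way, a cross-reference from the row is enough. The cost is a sentence or two of SAP text and a small programming edit before database lock. No new data are needed, and no alpha-controlled analysis changes.

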		
the control-based imputation method, we will separate our data into two datasets: DATAIN_MONO_IMP12, containing all placebo subjects and those subjects from the CVC arm that have values at time-point Month 12 missing; and DATAIN_MONO_REST12, containing the rest of the subjects from the CVC arm (those with non-missing SCORE_12).
 
We will now call PROC MI to impute missing data at time-point Month 12 based on the model estimated exclusively from placebo subjects with non-missing values at time-point Month 12.
 <pre>proc mi data=DATAIN_MONO_IMP12 seed=234 nimpute=100 out= DATAIN_REG_IMP12 class outcome ; var <explanatory> outcome; monotone logistic (outcome= <explanatory>); run;</pre> 
The following data step assembles back a dataset containing all subjects.
 <pre>data DATAIN_IMP1; set DATAIN_MONO_REST1 DATAIN_REG_IMP1; run;</pre> 
Data from each imputation will be analyzed using CMH and results will be combined using following codes.
 <pre>PROC FREQ DATA=DATAIN_IMP1; TABLES stratification * trt * outcome / CMH; ODS OUTPUT CMH=cmh2; BY _Imputation_; RUN;</pre> <pre>DATA cmh_wh2; SET cmh2(WHERE=(AltHypothesis="General Association")); cmh_value_wh=((VALUE/DF)**(1/3) - (1-2/(9*DF)))/ SQRT(2/ (9*DF)); cmh_sterr_wh = 1.0; RUN;</pre> <pre>*** Combine results; PROC MIANALYZE DATA=cmh_wh2; ODS OUTPUT PARAMETERESTIMATES=mian_cmh_wh2; MODELEFFECTS cmh_value_wh; STDERR cmh_sterr_wh; RUN;</pre> <pre>*** Compute one-sided p-value; DATA mian_cmh_wh_p; SET mian_cmh_wh2; IF tValue > 0 THEN Probt_upper = Probt/2; ELSE Probt_upper = 1-Probt/2; RUN;</pre>

Parameter type	Timing	Missing Data Handling

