		
statistics obtained from each imputed dataset can be normalized using the above formula and the normalized values can let be input for PROC MIANALYZE in order to obtain combined results for these chi-square based tests.
 <pre> DATA _tmc_tests1; set _tmc_tests; *** ChiSq is a chi-square distributed statistic (e.g., logrank) and DF is its corresponding degrees of freedom as produced by PROC LIFETEST ***; ChiSq_wh=((ChiSq/DF)**(1/3) - (1-2/(9*DF)))/SQRT(2/(9*DF)); ChiSq_stderr_wh = 1.0; run; proc sort data=_tmc_tests1; BY _Imputation_; run; proc MIANALYZE data=_tmc_tests1; modeleffects ChiSq_wh; stderr ChiSq_stderr_wh; ods output parameterestimates=resprefix._tests; run; *** Combining results of Cox regression and exponentiation of the combined log-hazard ratios: Cox regression model parameter estimates from PROC PHREG represent log hazard ratios. They are normally distributed and do not need any further transformation to be combined with Rubin's rules using PROC MIANALYZE. However, the end results need to be exponentiated to obtain the numerical values of the hazard ratios and associated confidence intervals. proc phreg data=_tmc_1; by _Imputation_; class trtvar <classvars>; model timevar * censvar(censval) = trtvar covars / risklimits ties=efron rl; ods output ParameterEstimates=_es; run; /* Combine model coefficients. */ proc sort data=_es; by Parameter ClassVal0 _Imputation_; run; proc MIANALYZE data=_es; by Parameter ClassVal0; modeleffects Estimate; stderr stderr; ods output ParameterEstimates = _es_mianal; run; /*Exponentiate in order to obtain hazard ratio estimates and confidence intervals */ data resprefix. hr; </pre>

Parameter type	Timing	Missing Data Handling
		<pre>set_es_mianal; Log_HR_comb=Estimate; HR_comb=exp(Estimate); HR_LCL_comb=exp(LCLMean); HR_UCL_comb=exp(UCLMean); keep Parameter ClassVal0 Log_HR_comb HR_comb HR_LCL_comb HR_UCL_comb Probt; rename Probt=HR_pval_comb; run;</pre>

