5.2 Changes in the Conduct of the Study or Planned Analyses

5.2.1 Changes in the Conduct of the Study

Approximately 1200 randomized participants were planned for the Part 1 analyses. During the actual study execution during the screening period for Part 1, 1293 participants were randomized into Part 1. This affects the newly randomized subject enrollment numbers anticipated for Part 2, as the number newly randomized in Part 2 will be decreased from approximately 800 to approximately 707. However, the total number randomized remains the same:

Arm	Newly Randomized Subjects in Part 2 N	Total Subjects (Randomized in Part 1 or Part 2) N	Treatment
A	472	1334	CVC 150 mg, once daily
B	235	666	Placebo, once daily

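### SAP Table 5-4: the Part 1 missing-not-at-random code leaves CVC completers out of every imputed analysis, and the Part 2 combined log-rank omits the upper-tail step used in Part 1

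*SAP*

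**What the plan says.** SAP 5.1.1.1.5, Table 5-4, gives SAS code for the multiple-imputation sensitivity analyses of both primary endpoints.

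**Part 1, missing not at random (control-based imputation).** The subjects are split in two:
- one data set is "DATAIN_MONO_IMP12, containing all placebo subjects and those subjects from the CVC arm that have values at time-point Month 12 missing";
- the other is "DATAIN_MONO_REST12, containing the rest of the subjects from the CVC arm", meaning those with an observed Month 12 value.

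Only the first goes to PROC MI (100 imputations), with output named DATAIN_REG_IMP12. The SAP then states: "The following data step assembles back a dataset containing all subjects". The code for that step is "data DATAIN_IMP1; set DATAIN_MONO_REST1 DATAIN_REG_IMP1; run". PROC FREQ runs the CMH test BY `_Imputation_`, and the Wilson-Hilferty values are combined in MIANALYZE. The result is converted to an upper-tail p-value: "IF tValue > 0 THEN Probt_upper = Probt/2", with one minus that half otherwise. The Part 1 missing-at-random block has the same conversion.

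**Part 2, informative censoring.** The log-rank chi-squares are transformed in the same way and combined, and the block ends at "modeleffects ChiSq_wh; stderr ChiSq_stderr_wh; ods output parameterestimates=resprefix._tests; run". No tail conversion follows. A separate block combines the Cox log hazard ratios and keeps the two-sided p-value ("rename Probt=HR_pval_comb"), which is correct for a normally distributed estimate.

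**The concern.** **Part 1.** There are two faults, one behind the other. The SET statement reads DATAIN_MONO_REST1 and DATAIN_REG_IMP1, but the data sets created end in 12, so the step stops. Once the names are corrected, the completers are still stacked only once and carry no `_Imputation_` value. BY processing puts them in a group of their own, with one treatment arm and no comparison to make. Imputations 1 to 100 then hold placebo and the CVC non-completers only. This is the only missing-not-at-random method specified for the Part 1 primary endpoint, and its output would not depend on the observed CVC response. A robust primary result would look fragile.

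**Part 2.** The transformed value is a normalised chi-square, so evidence against the null lies only in the upper tail. A two-sided p-value is twice the right value when z is positive, and is too small when z is strongly negative. The reported log-rank p could fall on the other side of a significance level and disagree with the Cox p from the same imputations.

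**Working it through.** **Planning figures reproduced**
- Part 1 (SAP 5.1.2: 800/400, 25% vs 15%, two-sided 0.0012), normal test with unpooled variance: 0.10 / √(0.15×0.85/400 + 0.25×0.75/800) = 4.25; 4.25 − 3.24 = 1.01; power 84.4% (stated 84%).
- Part 2 (367 events, HR 0.62, 2:1): expected z = √(367×2/9) × |ln 0.62| = 4.32; power 86.2% at 0.00125 (stated 85%) and 99.1% at 0.05 (stated 99%).

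**(a) Part 1: who is in each imputed analysis**
- SAP 5.1.2 expects 15% missing. With 15% in each arm, 0.15 × 800 = 120 CVC subjects enter PROC MI and 680 do not. Each imputed CMH holds about 400 + 120 = 520 of 1200 subjects.
- SAP 5.2.1 reports that "1293 participants were randomized into Part 1". Its table implies 1334 − 472 = 862 CVC and 666 − 235 = 431 placebo. Then about 129 of 862 CVC subjects are used.

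Simulation assumptions: 15% missing in both arms; response 25% vs 15% with missing counted as non-response (25/0.85 and 15/0.85 among those observed); imputation from placebo completers within the four strata; 100 imputations; CMH per imputation; Wilson-Hilferty, Rubin's rules and upper-tail p; 1000 trials for the first two rows, 300 for each of the others.

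| Scenario | Median p, names repaired only | Median p, all subjects | Share < 0.048 (names only / all) |
|---|---|---|---|
| 800/400 | 0.49 | 0.0004 | 0% / 97% |
| 862/431 | 0.49 | 0.0002 | 0% / 98% |
| 862/431, 10% missing | 0.49 | 0.0002 | – |
| 862/431, 25% missing | 0.49 | 0.0005 | – |
| 862/431, 40% CVC response | 0.49 | < 0.00001 | – |

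At 800/400 the smallest p with only the names repaired was 0.40. A separate simulation (150 trials, 30 imputations) gave 523 subjects per imputed group, 677 completers in the unnumbered group, and median p of 0.49 against 0.0003. The p-value stays near one half because both sides of the comparison come from the placebo response distribution.

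**(b) Part 2: size of the missing tail step**

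With 1 degree of freedom, z = (X^(1/3) − 7/9) / √(2/9). Between-imputation variance is ignored.

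| Chi-square | True p | z | Two-sided output | Upper tail |
|---|---|---|---|---|
| 3.841 | 0.05 | 1.672 | 0.094 | 0.047 |
| 10.415 | 0.00125 | 2.983 | 0.0029 | 0.0014 |
| 0.455 | 0.50 | −0.018 | 0.985 | 0.507 |
| 0 | 1 | −1.650 | 0.099 | 0.95 |

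The output is not monotone: no difference at all (chi-square 0) gives 0.099. It falls below the true p when chi-square is under 0.188 (z below about −0.43, true p above 0.66).

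Chi-square at which the two-sided output reaches each level:
- 0.05: (1.960 × 0.4714 + 0.7778)³ = 4.928, true p 0.026.
- 0.00125: (3.227 × 0.4714 + 0.7778)³ = 12.153, true p 0.0005.

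So the conclusion changes for true p of about 0.026 to 0.05, or 0.0005 to 0.00125. With the tail step, the strict level is reached at chi-square 10.692 (true p 0.0011). The remaining gap up to 0.00125 is Wilson-Hilferty approximation error.

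**The case against.** The strongest reply is that this is template code under correct prose. The missing-at-random block is offered as example code with placeholders, and the imputation variables were still to be fixed in a SAP amendment. The text requires all subjects after re-assembly, and Table 5-2 sets all subjects as the default for responder analyses. The name error would stop the program, and a programmer who then saw about 520 of 1200 subjects per analysis should notice. SAS was not run, so what its log would show is untested.

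For Part 2, the block never says that the two-sided value is the one to report, and the tail step is printed twice in the same table. No alpha level is attached to this sensitivity analysis. At the planned 367 events and HR 0.62, the chance of landing in the affected window is small: 99.1% − 98.2% = 0.9% at 0.05, and 86.2% − 79.7% = 6.5% at 0.00125.

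Much of this is fair on likelihood and impact. It does not remove either fault. The missing-not-at-random block is worded more literally than the missing-at-random one, and nothing in it carries the completers into the imputations. A missing `_Imputation_` sorts first and the completers are listed first in the SET, so no sort error would be expected. In Part 2, a programmer following the code has only a two-sided p-value to report.

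**Conclusion.** Both errors stand. With only the data set names repaired, the Part 1 missing-not-at-random analysis leaves out about 85% of the CVC arm and cannot show an effect whatever the true CVC response: median p about 0.49, against 0.0004 (800/400) or 0.0002 (862/431) when all subjects are included. The Part 2 combined log-rank output is about twice the correct p-value in the range of interest.

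The scope is limited. The primary CMH and log-rank tests, the Part 1 missing-at-random analysis and the Part 2 Cox result are unaffected, and neither error inflates type I error in the range that matters. This should be corrected, but it does not threaten the primary conclusions. The Part 1 sizes rest on the simulation assumptions above, although the median p stayed at 0.49 across 10% to 25% missing and up to a 40% CVC response. The Part 2 sizes assume no between-imputation variance.

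**What to change.** - **Part 1:** align the data set names. Output each CVC completer once for every `_Imputation_` from 1 to 100 before the SET, and sort by `_Imputation_`. Check that every imputation contains all mITT subjects before PROC FREQ runs.
- **Part 2:** add the Part 1 upper-tail conversion after the log-rank MIANALYZE step and name that value as the reported p-value.
- **Clarification in the same block:** state that the per-imputation log-rank uses the fibrosis-stage and T2DM strata of the primary test. Table 5-2 already implies this, but the only PROC LIFETEST code shown, which estimates the survival functions, has treatment arm alone in its STRATA statement.

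The cost is a few lines of SAP code, with no change to data or design. It is best done before the Part 1 unblinding.
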